3.4.3.15 Change from baseline to Weeks 16 and 24 in ACQ-6

Change from baseline to Week 16 and to Week 24 in ACQ-6 will be summarized separately by treatment group using descriptive statistics including number of subjects, mean, median, SD, minimum, and maximum.

3.4.3.16 Subjects requiring rescue therapy during the treatment and follow-up period

The number and percentage of subjects requiring rescue therapy during the treatment period will be summarized by visit. Similarly, the number and percentage of subjects requiring rescue therapy during the treatment period and the follow-up period will also be summarized. In addition, a plot of the cumulative proportion of subjects receiving rescue therapy during the treatment and follow-up periods will be provided.

3.4.3.17 Time to first use of rescue therapy

Summary descriptive statistics (including number, minimum, maximum, median, 25th and 75th percentiles) will be provided for time to first use of rescue therapy either during the treatment or follow-up period. In addition, Kaplan-Meier analysis of the time to first use of rescue therapy will also be performed.

3.4.3.18 Incidence of skin infection TEAEs

The incidence of skin infection TEAEs requiring systemic treatment during the treatment and follow-up periods will be summarized descriptively by treatment group.

3.5 Biomarker Analyses

3.5.1 Blood Concentration of sST2 and CCI

The blood concentration of soluble ST2 (sST2) will be summarized by visit using descriptive statistics (number, mean, geometric mean, SD, median, coefficient of variation, minimum, and maximum). Change from (or ratio to) baseline to Week 16 in the concentrations of sST2 will be summarized descriptively by visit as described above. The concentration values will be log-transformed and analysis of change from baseline to Week 16 of the log-transformed data will be performed using an ANCOVA model. The model will include treatment group and randomization stratum (total serum IgE < 150 kU/L or ≥ 150 kU/L) as categorical factors, with baseline sST2 as a covariate. The restricted maximum likelihood (REML) approach will be used for the estimation of the variance and covariance parameters of the linear mixed model. No imputation will be made for missing data. The results obtained will be back-transformed to the original scale. The estimated adjusted mean ratio to baseline (± standard error) for each treatment group will be provided. Also, the ratio of the adjusted mean ratio of each MEDI3506 group to placebo will be provided along with the 90% CI and p-value. The change from baseline to Week 16 in blood concentration of CCI will be explored and reported separately to the CSR.

3.5.2 Peripheral Blood Mononuclear Cell (PBMC) subset

The change from baseline in levels of PBMC subsets in whole blood at Week 16 may be explored and reported separately to the CSR.

3.5.3 Blood biomarker levels of Eosinophils, IL-33 bound to MEDI3506, IL-5, IL-13 and CCL17

Blood biomarker levels of eosinophils and IL-33 bound to MEDI3506 will be summarized descriptively (number, mean, geometric mean, median, coefficient of variation, minimum, and maximum) by visit for each treatment group. Change from (or ratio to) baseline to Weeks 1, 2, 4, 8, 12, 16, 20, and 24 in eosinophils and change from baseline to Weeks 1, 2, 4, 16, 20 and 24 in IL-33 bound to MEDI3506 will also be summarized descriptively by visit and treatment group for each biomarker. In addition, for IL-33 bound to MEDI3506, the levels will be log-transformed and analysis of change from baseline to Week 24 of the log-transformed data will be performed using a MMRM as described for the percent change from baseline to Week 16 in EASI score (Section 3.4.1.3). The results obtained from the model will be back-transformed to the original scale. The estimated adjusted mean ratio to baseline (\pm standard error) for each treatment group will be provided. Also, the ratio of the adjusted mean ratio of each MEDI3506 group to placebo will be provided along with the 90% CI and p-value. The mean (\pm standard error) change from baseline through to Week 16 and to Week 24 for IL-33 bound to MEDI3506 of the log-transformed data will be plotted for each treatment group separately for each biomarker. For eosinophils, the analysis will be done on the original scale, that is, no log-transformation will be performed for this biomarker. The change from baseline up to Week 24 in levels of IL-5, IL-13 and CCL17 will be explored and reported separately to the CSR.

3.5.4 Serum IgE levels and Plasma Eosinophil Derived Neurotoxin (EDN) levels

Descriptive summary statistics (number, geometric mean, median, coefficient of variation, minimum, and maximum) will be provided separately for serum IgE levels and plasma EDN levels by visit and treatment group. Change from baseline to Weeks 2, 8, 16, and 24 in serum IgE levels and to Weeks 4, 16, and 24 in plasma EDN levels will be summarized descriptively by visit for each treatment group. In addition, the IgE levels and EDN levels will be log-transformed and similar analysis described in Section 3.5.1 above will be performed on the log-transformed data. Also, a plot of mean change (\pm standard error) from baseline through to Week 24 of log-transformed IgE levels and EDN levels will be provided.

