Biomarkers	To evaluate the effect of MEDI3506 on blood biomarkers that may either predict or reflect an efficacy response in adult subjects with moderate-to-severe AD.	 Change from baseline to Week 16 in serum concentrations of: sST2. CCI Change from baseline to Week 16 in whole blood PBMC subsets Change from baseline to Weeks 1, 2, 4, 8, 12, 16, 20, and 24 in serum biomarker levels, including but not limited to: Eosinophils. IL-5. IL-13. CCL17. Change from baseline to Weeks 1, 2, 4, 16, 20 and 24 in serum IL-33 bound to MEDI3506 Change from baseline to Weeks 2, 8, 16, and 24 in serum IgE levels. Change from baseline to Week 16 in proinflammatory gene signatures in whole blood. Change from baseline to Weeks 4, 16, and 24 in plasma EDN levels.
Biomarkers	To evaluate the effect of MEDI3506 on skin biomarkers that may either predict or reflect an efficacy response in adult subjects with moderate-to-severe AD.	 Colonization of pathogenic bacteria (ie, Staphylococcus aureus) in lesional and non-lesional skin, from baseline to Week 16. From baseline to Week 16 in lesional and non-lesional skin: Proinflammatory gene signatures in tape strips and biopsies. Gross inflammation evaluation.
Efficacy	To assess the effect of MEDI3506 compared with placebo on the need for rescue therapy, in adult subjects with moderate-to-severe AD.	 Proportion of subjects requiring rescue therapy during the treatment and follow-up periods. Time to first use of rescue therapy throughout the treatment and follow-up periods. Incidence of skin infection TEAEs requiring systemic treatment during the treatment and follow-up periods.

Table 3 Exploratory Objectives and Endpoints

Type	Objective	Endpoint
Efficacy	To evaluate the effect of MEDI3506 compared with placebo on nasal symptom control, in a subset of adult subjects with moderate-to-severe AD who have comorbid chronic inflammatory conditions of the nasal mucosa and/or paranasal sinuses.	Change from baseline to Week 16 and 24 in SNOT-22.
Efficacy	To evaluate the effect of MEDI3506 on asthma symptom control compared with placebo, in a subset of adult subjects with moderate-to-severe AD who have comorbid asthma.	Change from baseline to Week 16 and 24 in ACQ-6.
	CCI	

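### SAP 3.5.4 sends the repeated markers IgE and EDN to a Week 16-only ANCOVA, so 5 of 7 endpoint time points get no modelled ratio to placebo; a cheap, low-priority fix

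*SAP*

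**What the plan says.** Protocol 2.3 (Table 3) lists as exploratory endpoints "Change from baseline to Weeks 2, 8, 16, and 24 in serum IgE levels" and "Change from baseline to Weeks 4, 16, and 24 in plasma EDN levels". SAP 3.5.4 keeps those visits. It gives descriptive summaries by visit and treatment group, plus a plot of mean change through Week 24. For modelling it says only "similar analysis described in Section 3.5.1 above will be performed on the log-transformed data".

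SAP 3.5.1 specifies that "analysis of change from baseline to Week 16 of the log-transformed data will be performed using an ANCOVA model". The factors are treatment group and IgE stratum, "with baseline sST2 as a covariate". There is no visit term, and missing data are not imputed. The output is each active group's ratio to placebo with a 90% CI and p-value. The same paragraph adds that REML "will be used for the estimation of the variance and covariance parameters of the linear mixed model".

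SAP 3.5.3 treats IL-33 bound to MEDI3506, also measured at several visits, differently: "the levels will be log-transformed and analysis of change from baseline to Week 24 of the log-transformed data will be performed using a MMRM", as in 3.4.1.3.

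**The concern.** Section 3.5.1 suits sST2, which has one post-baseline endpoint time. IgE has four and EDN has three. If the cross-reference is followed literally, the modelled comparison covers Week 16 alone. The early visits have no adjusted estimate, nor does Week 24, which falls 12 weeks after the last dose (Week 12, SAP 2.2). A subject with earlier samples but none at Week 16 contributes nothing to the model.

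Two features suggest the reference was not revisited when 3.5.1 took its present form. One is the REML sentence, which describes a model that 3.5.1 no longer contains. The other is in the protocol's amendment log (background only), which attributes the sST2 change from a repeated-measures model to ANCOVA to the removal of time points. That reason does not apply to IgE or EDN.

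At stake are the completeness of two exploratory biomarker analyses and whether two programmers would fit the same model from this text. No primary, secondary or safety conclusion depends on it.

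**Working it through.** The documents give no power or precision figure for IgE or EDN, so there is none to reproduce.

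**1. Coverage.** Visits are from Protocol Table 3 and SAP 3.5.4.

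- Endpoint time points: IgE 4 + EDN 3 = 7.
- Covered by a Week 16 ANCOVA: 1 + 1 = 2.
- Not modelled: 7 − 2 = 5 (IgE Weeks 2, 8, 24; EDN Weeks 4, 24).

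**2. Precision at Week 16.** The documents give neither the missing fraction nor the correlations, so both are assumed. Let m be the fraction of Week 16 samples missing (10–30%). Let r be a common correlation among baseline, one earlier visit and Week 16 on the log scale (0.5–0.9). The ANCOVA already uses baseline, so the earlier visit adds only its partial correlation given baseline:

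ρ = (r − r²)/(1 − r²) = r/(1 + r)

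- ANCOVA variance ∝ 1/(1 − m)
- MMRM variance ∝ ρ² + (1 − ρ²)/(1 − m)
- MMRM/ANCOVA variance = 1 − mρ², so the MMRM standard error is lower by 1 − √(1 − mρ²)

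| r | ρ | m = 10% | m = 20% | m = 30% |
|---|---|---|---|---|
| 0.5 | 0.333 | 0.6% | 1.1% | 1.7% |
| 0.7 | 0.412 | 0.9% | 1.7% | 2.6% |
| 0.9 | 0.474 | 1.1% | 2.3% | 3.4% |

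The formula uses one earlier visit. IgE has two (Weeks 2 and 8). With the same equal correlations, ρ² is replaced by 2ρ²/(1 + ρ). At r = 0.9 that is 2 × 0.2244/1.4737 = 0.3045, and at m = 30% the reduction is 1 − √(1 − 0.3 × 0.3045) = 4.7%. The gain stays small.

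**3. Bias at Week 16.** Assume that, in placebo only, subjects in the top third of an earlier value are lost with probability 0.5 and the others with 0.1. Take log SD 0.6–0.8 and r 0.5–0.9.

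- Overall loss: (0.5 + 2 × 0.1)/3 = 23%.
- Completers' mean of the earlier value is shifted by about −0.19 SD.
- Completers' baseline and Week 16 means each shift by about −0.19r SD. Adjusting for baseline with slope about r leaves −0.19 × r(1 − r) SD.
- Largest: r = 0.5, SD 0.8: 0.19 × 0.25 × 0.8 = 0.038 log units.
- Smallest: r = 0.9, SD 0.6: 0.19 × 0.09 × 0.6 = 0.010 log units.
- On the ratio scale: e^0.010 = 1.010 and e^0.038 = 1.039, so about 1–4% too high.

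Fitting the ANCOVA to simulated data under these assumptions gave the same range, 0.010–0.038. With the same loss rule in both arms the shifts cancel and the contrast is unbiased. An MMRM that includes the earlier visit is valid under this kind of loss, because loss depends only on observed values.

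**The case against.** **The protocol promises less than the SAP delivers.** Protocol 4.8.6 commits only to by-visit summaries for IgE and EDN and leaves further analysis to the SAP. The SAP gives those summaries and adds a model. Week 16 is the primary endpoint visit, and one modelled comparison per exploratory marker limits the number of p-values. This stands: there is no breach of the protocol, and a Week 16-only model would be defensible if the SAP stated it.

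**The wording leaves room.** The SAP calls for a *similar* analysis, and 3.5.1 still mentions a linear mixed model. A per-visit ANCOVA or a repeated-measures model is not excluded. This also stands, but it shows that the model is not uniquely specified, which needs the same edit. Nor should the text be read as putting baseline sST2 into an IgE model; *similar* implies the marker's own baseline.

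**The comparator is only one marker.** Section 3.5.3 expressly assigns the MMRM to IL-33 bound to MEDI3506. For eosinophils, also repeated, it says only that the original scale is used. So the MMRM is a precedent within the SAP, not a uniform rule.

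**Stronger readings that the documents do not support.**

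- A reader might infer that five time points have no comparison with placebo, or that subjects without Week 16 data vanish. Summaries by group, placebo included, are given at every listed visit, and those subjects stay in the summaries for the visits they attended.
- A reader might infer a material loss of precision or bias. Leaving baseline out of the calculation gives a standard-error difference of 1–13% and, with placebo-only loss, a ratio 6–15% too high. Those figures describe an unadjusted Week 16 mean, not the ANCOVA in 3.5.1.
- Nothing in the documents points to marker-driven loss in one arm. Protocol 4.7.4 asks all subjects to complete the visit schedule whether or not they stay on treatment, and 3.5.1 does not exclude post-rescue samples.

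**Conclusion.** The point holds in a limited form. On the plain text, 2 of 7 IgE and EDN endpoint time points get a model-based ratio to placebo and 5 do not, and subjects without a Week 16 sample leave the model though not the summaries. That count rests on the documents alone.

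The cost at Week 16 itself is small. The MMRM standard error would be about 0.6–3.4% lower, assuming 10–30% missing, equal correlations of 0.5–0.9 and one earlier visit. The ratio would be about 1–4% off under the assumed placebo-only loss and unbiased if loss is the same in both arms. The case for changing the text is therefore coverage of the stated visits and a single clear specification, with only a slight gain in precision or bias. For an exploratory endpoint this is a low-priority improvement.

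**What to change.** In SAP 3.5.4, replace the reference to 3.5.1 with the MMRM already used in 3.5.3 and 3.4.1.3, on the log scale. Include treatment, IgE stratum, visit, treatment-by-visit, the marker's own log baseline and log baseline-by-visit. Name the visits: Weeks 2, 8, 16 and 24 for IgE; Weeks 4, 16 and 24 for EDN. Report the back-transformed ratio to placebo with 90% CI at each visit. State whether the exclusion of post-rescue data in 3.4.1.3 carries over, since 3.5.1 has no such rule and the new reference would otherwise import it silently.

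In SAP 3.5.1, delete the sentence on REML and the linear mixed model; the ANCOVA for sST2 stays.

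The cost is a few lines of text, a little programming that reuses the MMRM code, and no new data. If p-values are reported at each visit, three active groups at 7 instead of 2 time points means 21 instead of 6, so 15 more unadjusted exploratory p-values, to be labelled nominal. If Week 16 alone is really intended, one sentence saying so would remove the ambiguity but leave the other five time points descriptive.

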3.5.5 Proinflammatory Gene Signatures in Blood

Change from baseline to Week 16 in proinflammatory gene signatures in whole blood will be reported separately from the CSR.

3.5.6 Colonization of Pathogenic Bacteria in Lesional and Non-lesional Skin

Colonization of pathogenic bacteria (ie, *Staphylococcus aureus*) in lesional and non-lesional skin at baseline and Week 16 will be summarized by visit using descriptive statistics (number, geometric mean, median, coefficient of variation, minimum and maximum). In addition, change from baseline to Week 16 in colonization of pathogenic bacteria (ie, *Staphylococcus aureus*) in lesional and non-lesional skin will be summarized using descriptive statistics by visit for each treatment group.

3.5.7 Gross inflammation evaluation

Gross inflammation evaluation in lesional and non-lesional skin at baseline and Week 16 may be explored and reported separately to the CSR.

3.5.8 Proinflammatory Gene Signatures in Lesional and Non-lesional Skin

The data on proinflammatory gene signatures in lesional and non-lesional skin at baseline and Week 16 will be assessed by the Translational Science (TS) group and the effect of the gene signatures on the primary efficacy endpoint will be explored and reported separately from the CSR.

3.5.9 CCI [REDACTED]

CCI [REDACTED]

3.6 Safety Analyses

3.6.1 Adverse Events and Serious Adverse Events

Adverse events (AEs) will be coded by Medical Dictionary for Regulatory Activities (MedDRA) by system organ class (SOC) and preferred term (PT). The type, incidence, severity and relationship to study investigational product will be summarized by treatment group. Specific adverse events will be counted once for each subject for calculating percentages. In addition, if the same adverse event occurs multiple times within a particular

subject, the highest severity and level of relationship observed will be reported. The number and percentages of participants will also be summarized by SOC and PT for participants with COVID-19 related AEs and SAEs. All treatment-emergent adverse events (TEAEs) will be summarized overall, as well as categorized by MedDRA SOC and PT. A TEAE is any new sign, symptom, disease, or other untoward medical event that begins or worsens after the first dose of investigational product up to the FU visit.

Summaries of adverse events will be presented by subjects who are COVID-19 positive or negative where a subject is COVID-19 positive if they have a TEAE in the MedDRA COVID-19 SMQ. Summaries will include TEAEs, TEAEs by MedDRA preferred term and SOC, SAEs, and adverse events of special interest (AESI).

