Subjects who are suspected (or known) to have COVID-19 should not be included, per Exclusion Criterion 10. Subjects who, during the course of the study, are suspected of having contracted COVID-19 should not be brought into contact with other subjects. If it is not possible for a subject to attend a study visit, then the patient should be contacted by telephone for the assessment of AEs, changes in concomitant medications, and other assessments that may be performed entirely verbally. Polymerase chain reaction testing for severe acute respiratory syndrome coronavirus 2 (SARS-CoV-2; the virus causing COVID-19) is not mandated for this study, as a subject with a negative result may become infected at any time after the sample was taken. Testing for COVID-19 may and should be performed, if required, by local / national guidelines.

It is recognized that depending on the location and facilities of a clinical site, study visit attendance may place subjects at risk of exposure to SARS-CoV-2. Furthermore, it is recognized that more general population level measures to reduce infection rates (eg, travel restrictions) may inhibit the ability of subjects to attend study visits. Necessary healthcare responses to the pandemic at sites (eg, additional infection control measures) may also inhibit the ability of a clinical site to effectively and properly conduct the study. Study visit attendance for dosing and for clinical assessments of treatment response are critical for the scientific value of the study.

Therefore, investigators should not enrol subjects unless they have reasonable confidence that throughout the duration of the study:

- Subjects will be able to attend study visits, whilst avoiding contact with concentrations of COVID-19 patients (eg, hospital entrances used by such patients) and
- The site will be able to effectively and safely conduct the study, considering relevant national and local factors.

The sponsor will conduct risk-based enrolment assessments on a country and site level, on a regular basis during the pandemic phase, and decisions will be documented.

All site staff should wear personal protective equipment in accordance with local or national guidelines.

The primary endpoint will be analyzed using a mixed-effects model for repeated measures (MMRM) which, in the event of missing data, uses all data that are available. The sponsor will monitor the number of discontinuations, withdrawals, missed visits, and other missing data.

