3.6.2 Adverse Events of Special Interest

The following are AESIs have been defined in the study protocol:

- Hepatic function abnormality meeting the definition of Hy's Law (HL), which is defined as any increase in alanine transaminase (ALT) or aspartate transaminase (AST) to greater than $3 \times$ upper limit of normal (ULN) and concurrent increase in total bilirubin (TBL) to greater than $2 \times$ ULN.
- Serious hypersensitivity (including Type 1 to 4 hypersensitivity reactions), including anaphylaxis and severe allergic reactions, and immune complex disease.
- Injection site reactions.
- Cardiac events (including angina or myocardial infarction, congestive heart failure, symptomatic atherosclerotic vascular disease, cor pulmonale, or arrhythmia).
- Serious infections (including opportunistic infections and viral reactivations), for example VZ/HSV, EBV/CMV, and TB.
- Gastrointestinal adverse events.
- Malignancy.

AEs will be assigned to a specific category based on investigator's judgement, using a checkbox on the AE CRF page. In addition, an AESI search strategy provided by Patient Safety will also be used to identify AESIs programmatically.

Subjects who meet the following criteria will be summarized by treatment group and separate listings of subjects will be presented:

- ALT/AST > 3 × ULN and any bilirubin > 2 × ULN
- ALT/AST > 5 × ULN for more than 2 weeks
- ALT/AST > 8 × ULN

All other AESIs will be summarized by treatment group and included in separate listings. In addition, the injection site reaction AE will be summarized by the placebo groups.

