3.0	08JUN2022	
 Removed interim analysis Added visit window calculation and updated visit window tables Updated IPD categories Added COVID-19 PD listings and summaries Added additional analyses excluding unblinded subjects (sections 3.4.1.4 and 3.4.2.3) Corrected MCP-Mod analysis of %change in EASI with LOCF to remove MMRM PGI-S categories updated to 6 Removed PGI-S MMRM analysis from section 3.4.2.2 Updated IGA and EASI 75 MCP-Mod analyses to use coefficients from logistic regression Appendix I- corrected IGA MCP-Mod analysis and added EASI75 Updated biomarker section Removed section 3.5.9 Responder subgroup identification Added equations for QTcB and QTcF Added additional ADA categories to section 3.7 Updated PK section (3.8) Changed S aureus subgroups to use median Added AESI search strategy in section 3.6.2 Changed screening window to 4 weeks Added Plasma EDN to baseline disease characteristic list and removed serum IgE (pos vs neg) Updated section 3.4.1.5 to remove sentences on subgroups Corrected SCORAD calculation Added extra biomarker endpoints to be reported separately to CSR Updated clinical lab evaluation section Added Other safety tests section to include NT-proBNP analysis Added ADA safety and efficacy tables Added COVID-19 pos/neg safety analysis 	
 To align with Protocol Amendment #7, #8 Clarification of how to calculate visit windows To align with other Medi3506 studies To align with Protocol Amendment #5 Sensitivity analysis for unblinded subjects Correction of method To match what is being collected Analysis not needed (not really continuous) Correction of method Correction of method Scope has changed Information is covered in section 5 Was missing To align with AZ process To align with AZ process Data is going to be continuous Requested by patient safety To align with PA #8 Update of list Covered in section 5 already Correction of error To align with endpoints in protocol To remove lab toxicities as analysis not needed Analysis was missing To evaluate safety profile To evaluate impact of COVID-19 on the safety profile

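### SAP 3.6.1 classes subjects as COVID-19 positive by a TEAE and then counts TEAEs by that status, so the any-TEAE row is 100% in positives by construction and the contrast should not be read as the effect of COVID-19

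*SAP*

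**What the plan says.** SAP 3.6.1 (Adverse Events and Serious Adverse Events) sets up a split of the safety tables by COVID-19 status. The classification rule is that "a subject is COVID-19 positive if they have a TEAE in the MedDRA COVID-19 SMQ". The content of the tables follows at once: "Summaries will include TEAEs, TEAEs by MedDRA preferred term and SOC, SAEs, and adverse events of special interest (AESI"). A TEAE is an event that "begins or worsens after the first dose of investigational product up to the FU visit", so one window both classifies the subject and counts the outcome. Incidence is at subject level: "Specific adverse events will be counted once for each subject for calculating percentages". No sentence removes COVID-19 query terms from the counts, and none limits the counts in positive subjects to events after infection.

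The purpose appears only in SAP section 7 (Version History): "To evaluate impact of COVID-19 on the safety profile".

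Four other places bear on the point:

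- SAP 3.6.1 also plans a separate COVID-19 table: "The number and percentages of participants will also be summarized by SOC and PT for participants with COVID-19 related AEs and SAEs".
- SAP 3.1 has every tabular summary presented by treatment group.
- SAP 3.6.2 lists an AESI category that a serious COVID-19 case could enter: "Serious infections (including opportunistic infections and viral reactivations), for example VZ/HSV, EBV/CMV, and TB".
- Protocol 1.6.1 says that PCR testing "is not mandated for this study, as a subject with a negative result may become infected at any time after the sample was taken", apart from testing that local or national guidelines require. COVID-19 status therefore rests largely on what is reported as an adverse event.

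**The concern.** Group membership is set by an event of the same kind as the outcome. A subject enters the positive column by having a TEAE, and the column is then summarised by the share of its subjects with a TEAE. The first row that a reader looks at is fixed before any data arrive. Rows lower in the table are not fixed, but they include the COVID-19 events that created the group.

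The split also follows a post-randomisation event with no timing rule. Events that began weeks before the infection count in the positive column, and subjects followed for longer have more opportunity to enter it.

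At stake is interpretation. Protocol 1.6 names serious infection as a potential risk of MEDI3506, so tables labelled by COVID-19 status will be read with attention. A reader who takes the difference between the two columns as what COVID-19 did to safety would be reading mostly the definition in the any-TEAE row, and partly the definition elsewhere.

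**Working it through.** The plan states no figure for these tables, so there is nothing to reproduce. The central result is set logic. The rates below are assumptions used only to show size, because the documents give neither a COVID-19 rate nor a TEAE rate.

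**Inputs.** Planned N is 152 (58 + 18 + 18 + 58 pooled placebo; protocol 4.1.1, SAP 2.4). Assumed: share of subjects with a COVID-19 TEAE, c = 5% to 20%; share with a non-COVID TEAE, p = 30% to 70%; background SAE rate, s = 5%; share of COVID-19 TEAEs that are serious, q = 0% to 10%.

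**1. Any-TEAE row.** Subjects with a TEAE in the COVID-19 query are a subset of subjects with any TEAE. So P(any TEAE | positive) = 1 exactly. The query terms are 0% in negatives, and each positive subject has at least one.

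**2. Size when COVID-19 has no effect on other events.** With independence, the negative column shows p and the gap is 1 − p. If query terms are left out of the counts, both columns show p.

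| p (assumed) | Positive | Negative | Gap as planned | Gap with terms omitted |
|---|---|---|---|---|
| 30% | 100% | 30% | 70 points | 0 |
| 50% | 100% | 50% | 50 points | 0 |
| 70% | 100% | 70% | 30 points | 0 |

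For example, with c = 10% and p = 50%, overall TEAE incidence is 1 − (0.90 × 0.50) = 55%. The planned split divides this into 100% and 50%, since 0.10 × 100% + 0.90 × 50% = 55%. Dropping the query terms in the full population gives 50%.

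**3. SAE row.** Under the same independence, the positive column is 1 − (1 − s)(1 − q) and the negative column is s. At s = 5%:

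- q = 0%: 5% against 5%.
- q = 5%: 1 − 0.95 × 0.95 = 9.75% against 5%.
- q = 10%: 1 − 0.95 × 0.90 = 14.5% against 5%.

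The row is inflated only if some COVID-19 events are serious. The AESI row behaves in the same way. Rows for preferred terms outside the query are not touched by the defining events.

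**4. Timing and follow-up, with query terms already removed.** This was simulated with constant hazards over 24 weeks, 10% COVID-19, 50% other TEAE, no link between the two, and dropout at a uniformly distributed time.

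| Dropout | Non-COVID TEAE, positive | Non-COVID TEAE, negative | Residual gap |
|---|---|---|---|
| 0% | 49.9% | 50.0% | about 0 |
| 10% | 49.3% | 47.6% | 1.7 points |
| 20% | 48.6% | 45.3% | 3.3 points |
| 30% | 47.5% | 43.1% | 4.4 points |

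About 55% of first non-COVID TEAEs in positive subjects came before COVID-19 onset, so they cannot be a consequence of it. Omitting the terms removes the large artefact but not all of the bias.

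**5. Size of the positive column.** 152 × c is 7.6 subjects at 5%, 15.2 at 10% and 30.4 at 20%. In an 18-subject arm that is 0.9 to 3.6 subjects.

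**The case against.** The strongest reply is that SAP 3.1 puts all tabular summaries by treatment group, so the display is MEDI3506 against pooled placebo within each status. By definition the COVID-negative tables contain no TEAE from the COVID-19 query, so they do offer a drug-placebo comparison without those events. The stated purpose can fairly be read as asking whether the drug's safety profile looks different once COVID-19 cases are set apart, and by-arm tables within status speak to that. This stands. A reader might infer that the tables cannot serve their purpose at all, or that no comparison free of COVID-19 events is planned. The documents support neither.

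The reply has a limit. Being COVID-negative is a post-randomisation outcome that treatment could influence: protocol 1.6 lists serious infection as a potential risk, and protocol 1.6.1 raises the possibility that blocking IL-33 helps in severe COVID-19. The negative stratum is therefore readable descriptively but is not a randomised comparison.

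A reader might also infer a false drug signal for serious infection, or a large excess of SAEs in positives. Neither follows. In the positive stratum the any-TEAE row is 100% in every arm that has a positive subject, so the definition creates no difference between arms there (and carries no information either). The main TEAE, SAE and AESI tables by treatment group are unchanged by the split. The SAE excess depends on how many COVID-19 events are serious, which the documents do not indicate.

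Finally, the separate COVID-19 event table lets a careful reader see what drives the positive column. That is true, but it does not correct the by-status counts.

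**Conclusion.** The point holds at minor severity. The any-TEAE row is 100% in positives by construction, and the COVID-19 query terms are 0% in negatives; both follow from SAP 3.6.1 alone, and nothing elsewhere in the SAP removes the overlap. The SOC rows that hold those terms, and the SAE and AESI rows, can be inflated by the COVID-19 events and can include events from before onset. They are contaminated rather than fixed. The positive-versus-negative contrast should therefore not be read as the effect of COVID-19 on safety.

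The gap of 30 to 70 points rests on assumed non-COVID TEAE rates of 70% down to 30% and on independence. The SAE and follow-up figures rest on the other assumptions stated in the working. These are descriptive tables: SAP 3.6.1 attaches no test or decision rule to them, and the efficacy analyses do not use them.

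**What to change.** Add TEAE, SAE and AESI tables by treatment group in the full As-treated population, leaving out events in the COVID-19 query. These keep every randomised and dosed subject, and they follow what SAP 3.3.2 already does for important protocol deviations, which are summarised both with and without those related to COVID-19. Keep the separate table of COVID-19 events.

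If the by-status display is kept, omit the query terms from its counts and say in the SAP whether the narrow or broad query is used. Add a footnote that events before COVID-19 onset are counted and that follow-up differs between the groups, so the columns should not be compared as an effect of COVID-19. With perhaps 8 to 30 positive subjects under the assumed rates, rates per person-time would add little, and a footnote is enough.

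The cost is a short change to SAP 3.6.1 and one extra table set to program. No new data are needed.
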